### 5.5 Analysis Software

Statistical processing will be performed using Statistical Analysis System (SAS®) 9.4. (Please refer section 6.0).

## 6.0 GENERAL CONSIDERATIONS FOR STATISTICAL ANALYSIS

The statistical analysis will be performed using the SAS version 9.4. The descriptive statistics for the continuous data will be presented using mean, standard deviation, standard error, median and 95% CI, whereas, for the categorical data it will be presented using number of observations (n) and percentages (%) For continuous data, normality will be tested though “Kolmogorov-Smirnov Goodness-of-Fit Test”. If normality assumption will not fulfil then non-parametric methods such as Mann Whitney U/ Kruskal Wallis Test will be used.

Following statistical tests/procedure will be performed wherever required:

#### **Clopper Pearson Method for Confidence Interval**

The Proc Freq procedure of SAS will be used to find the 95% CI:

ods output;

binomial = <name of dataset containing p-value>;

PROC FREQ data=<dataset name>;

by <list of categorical variables>;

tables<values of the categorical variables >/binomial alpha=<significant level>;

weight <count>;

exact binomial;

run;

**Title: Statistical Analysis Plan-Module I**

SOP Number:  
JSS-DM-BIS-01

Current Version Number: 1.0

Previous Version Number: Nil

Document Date:  
25MAR2021

ods output close;

**Proc mixed for MMRM ANCOVA Model**

proc mixed;

class var1 var2;

model var1 = var2;

random var1 var1\*var2;

run;

ods

**The Proc Means procedure of SAS will be used to find the summary statistics**

PROC means data=<dataset name>;

var < variable to be analyzed >;

OUTPUT OUT=<name of dataset containing all statistics>

N=n MEAN=mean STDERR=stderr LCLM=lclm UCLM=uclm;

ods

run;

**Chi-square Test**

The Proc Freq procedure of SAS will be used to find the p-value:

ods output;

Chi-square = <name of dataset containing p-value>;

PROC FREQ data=<dataset name>;

by <list of categorical variables>;

tables<values of the categorical variables >/CHISQ=<significant level>;

weight <count>;

run;

ods

ods output close;

**Fisher Test**

**Title: Statistical Analysis Plan-Module I**

SOP Number:  
JSS-DM-BIS-01

Current Version Number: 1.0

Previous Version Number: Nil

Document Date:  
25MAR2021

The Proc Freq procedure of SAS will be used to p-value:

ods output;

fisher = <name of dataset containing p-value>;

PROC FREQ data=<dataset name>;

by <list of categorical variables>;

tables<values of the categorical variables >/fisher=<significant level>;

weight <count>;

run;

ods output close;

Proc TTEST < options >;

class variable;

paired variables;

by variables;

var variables;

## **6.0 DEMOGRAPHICS AND OTHER BASELINE CHARACTERISTICS**

### **6.1 Demographics**

Demographic and baseline characteristics, including age, sex, race, weight, BMI, medical history and conditions, prior anti-psoriasis therapy, duration of disease and any other study-appropriate data (e.g. PASI, BSA, IGA) will be tabulated and summarized by treatment groups. In addition, following parameters (by both independent dermatologist and investigator) will be summarized by number and percentages:

Patients with PASI <20 and PASI  $\geq$  20.

Patients with IGA of 3 and IGA of 4

Patients with prior exposure to systemic therapy

Patients with prior exposure of biologics

	JSS Medical Research India Private Limited Data Management		
Title: Statistical Analysis Plan-Module I			
SOP Number: JSS-DM-BIS-01	Current Version Number: 1.0	Previous Version Number: Nil	Document Date: 25MAR2021

## 6.2 Prior and concomitant medication

Prior and concomitant medications will be summarized by treatment group. Prior medications are defined as treatments taken and stopped prior to first dose of study treatment. Any medication given at least once between the day of first dose of randomized study treatment and the last day of study visit will be a concomitant medication, including those which were started pre-baseline and continued into the treatment period.

All prior, concomitant and prior/ concomitant medications that were recorded on the CRF will be coded and summarized, according to the generic names using the WHO drug classification (WHODD) dated September 1, 2019 or later, using the number and percentage of subjects for safety population. A listing of all prior, concomitant and prior/ concomitant medications will also be provided.

## 6.3 Baseline and Screening Conditions

### 6.3.1 Baseline Medical History

Relevant medical history should be recorded and should include prior/current medical conditions, including psoriasis diagnosis, and abnormal physical exam findings or clinically significant laboratory abnormalities (excluding study disease-related abnormalities) from the baseline assessment. Medical/ surgical history will be coded according to the MedDRA dictionary version 22.1 or later and will be summarized using number (%) of subjects for safety population, corresponding subject data listing will also be provided.

### 6.3.2 Other Screening Assessments

Menstrual history of women, QuantiFERON TB-Gold test and viral serology that are assessed at screening only for inclusion and exclusion testing will not be presented separately. However, the frequency and percentage will be presented for patients who will be eligible to participate based on all screening conditions.

## 7.0 EFFICACY ANALYSES

### 7.1 Primary Efficacy Analysis

Summary statistics with 95% confidence interval will be presented for PASI. Comparison of percentage of patients achieving at least 75% reduction from Baseline

	JSS Medical Research India Private Limited Data Management		
Title: Statistical Analysis Plan-Module I			
SOP Number: JSS-DM-BIS-01	Current Version Number: 1.0	Previous Version Number: Nil	Document Date: 25MAR2021

PASI score (PASI-75) to Week 12 between treatment arm and placebo will be evaluated using Chi-square/Fisher's exact test with responder and non-responder psoriasis type. Also, 95% CI for the responders within treatment will be evaluated by using Clopper-Pearson method and 95% CI for treatment difference will be evaluated by using Miettinen-Nurminen method.

Additional sensitivity analysis will be tested by using Cochran-Mantel-Haenszel (CMH) test after adjusting the sites and baseline PASI score. The analysis will be performed on efficacy population. No multiplicity adjustments will be done for the primary analysis.

Two sets hypotheses will be tested,

1.  $H_0: P_1=P_0$  vs  $H_1: P_1 \neq P_0$
2.  $H_0: P_2=P_0$  vs  $H_1: P_2 \neq P_0$

Where,  $P_0$ ,  $P_1$  and  $P_2$  are the proportion of responders in placebo, 400 mg and 600 mg arms, respectively. Since, both hypotheses will be tested separately, no multiplicity adjustment will be done.

## 7.2 Secondary Efficacy Analysis

Comparison of percentage of patients achieving at least 75% reduction from baseline PASI (PASI-75) score at 4 and 8 weeks between test and placebo will be evaluated using Chi-square/ Fisher's exact test with responder and non-responder psoriasis type. Also, 95% CI for treatment and for treatment difference will be evaluated by Clopper-Pearson method and Miettinen-Nurminen method, respectively.

Comparison of percentage of patients achieving at least 50% reduction from baseline PASI (PASI-50) score at 4, 8 and 12 weeks between test and placebo will be evaluated using Chi-square/ Fisher's exact test with responder and non-responder psoriasis type. Also, 95% CI for treatment and for treatment difference will be evaluated by Clopper-Pearson method and Miettinen-Nurminen method, respectively.

Comparison of percentage of patients with Investigator Global Assessment (IGA) scores of 0 or 1 at 4, 8 and 12 weeks of treatment (end of treatment) between test and placebo will be evaluated using Chi-Square test. Also, 95% CI for treatment and for treatment difference will be evaluated by Clopper-Pearson method and Miettinen-Nurminen method, respectively.

	JSS Medical Research India Private Limited Data Management		
Title: Statistical Analysis Plan-Module I			
SOP Number: JSS-DM-BIS-01	Current Version Number: 1.0	Previous Version Number: Nil	Document Date: 25MAR2021

?

Absolute and percent change of PASI score at visit 4, 8 and 12 from baseline will be computed using given formula:

$$\% \text{Change of PASI Score for time T} = \frac{(\text{PASI score at T} - \text{PASI score at baseline})}{\text{PASI score at baseline}} * 100$$

where time T can be week 4, week 8 and week 12.

Summary statistics of absolute & percent change from baseline in PASI score at week 4, 8 and 12 will be presented as n, mean median, SD, SE and 95% confidence interval for mean. Comparison of percent change in PASI scores from baseline to week 4, week 8 and week 12 between treatment groups i.e., from AUR 400mg to placebo and AUR 600mg to placebo will be analyzed using analysis of covariance (ANCOVA) model with baseline scores included as a covariate.

### 7.3 Additional Analysis

Comparison of PASI-75 and PASI-50 at week 2, 6 and 14 by Chi-square/ Fisher's exact test also. Also, 95% CI for treatment and for treatment difference will be evaluated by Clopper-Pearson method and Miettinen-Nurminen method, respectively.

Comparison of percentage of patients achieving at least 90% reduction from baseline PASI (PASI-90) score at 2, 4, 6, 8, 12 and 14 weeks between test and placebo will be evaluated using Chi-square/ Fisher's exact test with responder and non-responder psoriasis type. Also, 95% CI for treatment and for treatment difference will be evaluated by Clopper-Pearson method and Miettinen-Nurminen method, respectively.

Comparison of percentage of patients achieving 100% reduction from baseline PASI (PASI-100) score at 2, 4, 6, 8, 12 and 14 weeks between test and placebo will be evaluated using Chi-square/ Fisher's exact test with responder and non-responder psoriasis type. Also, 95% CI for treatment and for treatment difference will be evaluated by Clopper-Pearson method and Miettinen-Nurminen method, respectively.

IGA responder (IGA of 0 or 1) will be compared across treatment groups at week 2, 6 and 14 by Chi-square/ Fisher's exact test also.

Absolute change in IGA, percent change in PASI & BSA and absolute change in DLQI will also be compared across treatment groups at week 2, 6 and 14 by ANCOVA with baseline as covariate

Percentage of patients achieving MCID ( $\geq 5$ -points reduction from baseline) in DLQI will be compared across the treatment groups by Chi-square/ Fisher's exact test at week 2, 4, 6, 8, 12 and 14

Percentage of patients achieving DLQI score of 0 or 1 at week 2, 4, 6, 8, 12 and 14 will be compared across the treatment groups by Chi-square/ Fisher's exact test

An analysis of combined active arms (i.e. 400 mg BID and 600 mg BID) vs. placebo arms will be done for PASI75, PASI90, PASI100 and IGA responders (i.e. IGA of 0 or 1) at week 4, 8 and 12 by Chi-square/ Fisher's exact test. For this assessment, only independent dermatologist evaluation will be considered.

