7.0 STUDY ENROLLMENT AND WITHDRAWAL

7.1 Inclusion Criteria

- 1. Confirmed diagnosis of chronic plaque-type psoriasis, diagnosed at least 6 months before screening
- 2. Psoriasis of at least moderate severity, defined as PASI≥12 and involved BSA≥10 % at screening and Day 1
- 3. Adult males or females, ≥ 18 to ≤ 65 years of age,
- 4. Ability to communicate well with the investigator and to comply with the requirements of the entire study
- 5. Willingness to give written informed consent (prior to any study related procedures being performed) and ability to adhere to the study restrictions and assessments schedule.

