### 3.2.6.3 Dermatology Life Quality Index (DLQI)

The Dermatology Life Quality Index (DLQI) is a 10-item general dermatology disability index designed to assess health-related quality of life in adult patients with skin diseases such as eczema, psoriasis, acne, and viral warts. Scores range from 0 to 30, and higher scores indicate greater health-related quality-of life impairment. Additionally, each subscale of the DLQI may be analyzed separately. In DLQI score, Minimal Clinically Important Difference (MCID) is considered as 5-points reduction from baseline. [7-8]

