#### 4.3.4 Efficacy population

Efficacy population will include patients who

- have a valid baseline and at least one post-baseline (follow up) assessment for
- PASI score by the independent dermatologist or withdrawal is associated with lack of effect by the patient before post-baseline assessment.
- do not have any major protocol or inclusion/exclusion violations,

Efficacy population will provide sample for analysis of primary, secondary and exploratory endpoints. For patients who dropped out during study treatment period due to any reason, data from the last efficacy assessment will be considered for the primary endpoint and other secondary efficacy endpoints relevant at other future time-points as per Last Observation Carried Forward (LOCF) approach.

Efficacy data collected solely based on the photographs without on-site examination by the investigator/independent dermatologist will not be considered for the analysis and this data will also be imputed with LOCF approach.

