#### 5.4 Methods for Withdrawals, Missing Data, and Outliers

In case of a patient's withdrawal from the study without any major protocol deviation, its values on subsequent visits will be considered missing.

The last observation carried forward (LOCF) method will be applied to all efficacy measurements (PASI score, IGA mod 2011 score, DLQI score etc.) when at least one post-baseline assessment is available. If all post baseline efficacy values are missing for one efficacy parameter then these missing values will not be imputed and this patient will be removed from the analysis of the corresponding variable, i.e. it might be that the number of patients providing data for one variable is smaller than efficacy population. If withdrawal prior to first post-baseline assessment is considered due to lack of effect of the study drug by the investigator, then the respective patient will be considered as non-responder in PASI and IGA responder analysis, and no change (i.e. post-baseline difference of 0) will be considered for percent or absolute change in PASI, IGA or DLQI parameters.

For missing safety variables, when repeat assessment data is available for the respective visit, then these repeat assessment data will be imputed. E.g. The hematology parameters are not available for Visit 4 for any patient and repeat hematology assessment is done prior to next scheduled visit, then hematology parameters during Visit 4 will be replaced with repeat assessment parameters. However, no values will be replaced if the parameter value is available. For example, if only ALT and AST are not available for a specific visit in biochemistry panel and repeat assessment prior to next visit is done with all liver function tests (ALT, AST, ALP, bilirubin, etc.), then only ALT and AST values will be replaced and other liver function values will not be replaced.

For the efficacy variables (PASI score, IGA mod 2011 score, DLQI score), no observed values will be considered as outliers. For safety parameters like vital signs, lab parameters etc., any value which is out of range will be summarized as observed. However, it will be checked whether it is a normal or abnormal finding and will be

	JSS Medical Research India Private Limited Data Management		
Title: Statistical Analysis Plan-Module I			
SOP Number: JSS-DM-BIS-01	Current Version Number: 1.0	Previous Version Number: Nil	Document Date: 25MAR2021

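### The additional DLQI 5-point responder analysis sets no baseline floor, so patients who start at 0–4 are non-responders by construction; the cost is a modest loss of power, of unknown size

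*SAP*

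**What the plan says.** SAP 7.3 (Additional Analysis) takes the "Percentage of patients achieving MCID", a drop of 5 points or more, and states that this outcome "in DLQI will be compared across the treatment groups by Chi-square/ Fisher's exact test at week 2, 4, 6, 8, 12 and 14". The threshold comes from SAP 3.2.6.3, where the "Minimal Clinically Important Difference (MCID) is considered as 5-points reduction from baseline". The same section gives the scale: "Scores range from 0 to 30".

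Three further provisions fix the denominator:

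- SAP 4.3.4: "Efficacy population will provide sample for analysis of primary, secondary and exploratory endpoints". Membership depends on a valid baseline, post-baseline PASI (or early withdrawal for lack of effect) and the absence of major violations. It does not depend on DLQI level.
- SAP 5.4: when every post-baseline value of a parameter is missing, "this patient will be removed from the analysis of the corresponding variable". A low baseline is not a ground for removal.
- Protocol 7.1: "Psoriasis of at least moderate severity, defined as PASI≥12 and involved BSA≥10 % at screening and Day 1". Exclusion criterion 3 in Protocol 7.2 adds IGA of 3 or 4. No criterion sets a minimum DLQI.

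A companion analysis in SAP 7.3 covers the "Percentage of patients achieving DLQI score of 0 or 1 at week 2, 4, 6, 8, 12 and 14".

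**The concern.** A patient with baseline DLQI of 0 to 4 can fall by 4 points at most. The chance of response is zero in every arm, whatever the drug does, yet the patient counts in the denominator. Such patients add no information on treatment and pull both rates towards zero, which narrows the difference between them.

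The SAP avoids this elsewhere. Section 7.4 limits the 4-point IGA reduction to patients with baseline IGA of 4, the only ones who can achieve it. Section 3.2.6.2 requires an IGA responder to improve by at least 2 points, and entry criteria guarantee room to improve on PASI and IGA. The 5-point DLQI analysis has no such safeguard.

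At stake is the size and power of one supportive quality-of-life comparison, made at six visits. SAP 9.1 treats P below 0.05 as significant, and SAP 1.0 says the planned analyses may be used in manuscripts or regulatory submissions.

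**Working it through.** **The plan's own figure.** There is none for this analysis. The only sample size calculation is for PASI 75: 7% against 35%, one-sided 0.05, 25 per arm, 80% power. The pooled normal approximation gives 79.9% power at 25 per arm, so that figure reproduces, but it does not bear on this point. I take from it only the 30 per arm after the dropout allowance.

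**Inputs**

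- From the documents: scale 0–30, threshold 5 points, 30 planned per arm, two-sided 0.05 (the SAP 9.1 threshold, read as two-sided).
- Assumed, because the documents give neither: responder rates of 30% (placebo) and 60% (active) among patients able to respond, and the share q with baseline 0–4.

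**Formulas**

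- All-patient rate in an arm = (1−q) × rate among those able to respond + q × 0.
- All-patient difference = (1−q) × (0.60 − 0.30).
- Risk ratio = (1−q)(0.60) / [(1−q)(0.30)] = 2.0 for any balanced q.
- Power = Φ{[d − 1.96·√(2p̄(1−p̄)/n)] / √[(p0(1−p0) + p1(1−p1))/n]}, where d = p1 − p0 and p̄ = (p0 + p1)/2. Here n = 30 for all patients, or 30(1−q), rounded, after restriction.

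**Example, q = 20%.** Six of 30 per arm cannot respond. Expected responders are 0.30 × 24 = 7.2 and 0.60 × 24 = 14.4. The difference is 7.2/30 = 24.0 points for all patients and 7.2/24 = 30.0 points for those able to respond. All-patient power: p̄ = 0.36, so (0.24 − 1.96 × 0.1239)/0.1200 = −0.02 and power is 49.0%.

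| q | All patients: difference (points) | All patients: power (n = 30) | Baseline ≥5: n per arm | Baseline ≥5: difference (points) | Baseline ≥5: power |
|---|---|---|---|---|---|
| 0 | 30.0 | 65.3% | 30 | 30.0 | 65.3% |
| 5% | 28.5 | 61.1% | 28 | 30.0 | 62.2% |
| 10% | 27.0 | 57.0% | 27 | 30.0 | 60.6% |
| 20% | 24.0 | 49.0% | 24 | 30.0 | 55.4% |
| 30% | 21.0 | 41.5% | 21 | 30.0 | 49.8% |

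**Check by exact enumeration of the chi-square test.** Power for all patients against restricted is 61.9% v 61.3%, 57.4% v 58.6%, 48.9% v 59.0% and 41.5% v 49.5% at q = 5, 10, 20 and 30%. The gain is absent at 5%, about 1 point at 10%, and clear only from the larger shares.

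**Other assumed rates, q = 20%.** For 25% v 65%, 40 points becomes 32 and power is 74.5% against 81.6% restricted. For 35% v 70%, 35 points becomes 28 and power is 59.8% against 69.1%.

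**Unequal q by chance.** With 3 of 30 low-baseline patients on placebo and 6 of 30 on active, the difference is 0.60 × 0.80 − 0.30 × 0.90 = 21 points. The reverse gives 0.60 × 0.90 − 0.30 × 0.80 = 30 points.

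**The case against.** The strongest case is that little depends on this analysis. The protocol's DLQI endpoint is change from baseline at weeks 4, 8 and 12. SAP 7.2 analyses it by ANCOVA with baseline as covariate, and SAP 7.3 does the same at weeks 2, 6 and 14. No 5-point threshold enters there. This stands: a reader might infer that the quality-of-life objective is compromised, and the documents do not support that.

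Second, q is unknown. Entrants have PASI of 12 or more, BSA of 10% or more and IGA of 3 or 4, and nothing shows that any of them will score below 5. This stands too: dilution is a possibility, not an established fact. That low-baseline patients are failures is also an inference from the endpoint wording and the population rules. The SAP does not say it in words.

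Third, the all-patient rate is a legitimate quantity: the share of treated patients who gain 5 points. The comparison is between randomised arms, so type I error is not inflated. Chance imbalance at baseline affects any unadjusted comparison. This is a reason to keep the all-patient result, but not to make it the only one.

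A reader might extend the point to the DLQI 0/1 analysis, because a patient who starts at 0 or 1 can count as a responder without change. That does not follow. The 0/1 outcome is a state at the visit, and such a patient can still worsen and become a non-responder. Dilution has not been shown there.

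Finally, SAP 1.0 allows exploratory analyses outside the plan, so a restricted version could be added later. It would then have to be labelled as unplanned.

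**Conclusion.** The point holds as a small design weakness in an additional analysis. As written, any Efficacy-population patient with baseline DLQI 0–4 is a non-responder by construction in the 5-point analysis. With a balanced share q the risk difference shrinks by (1−q) and power falls modestly. Under the assumed 60% v 30% at 30 per arm, the normal approximation puts the all-patient analysis 1 to 4 percentage points of power below the restricted one at q = 5–10% (the exact test shows −1 to +1), and 6 to 8 points below at 20–30% (8 to 10 by the exact test). The effect is nil if q = 0.

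These sizes rest on assumed rates, an assumed q, equal q in both arms and 30 analysed per arm. It would be an improvement to the plan, not the correction of an error that threatens a listed endpoint.

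**What to change.** Before unblinding, add to SAP 7.3:

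- The main denominator for the 5-point DLQI responder analysis is Efficacy-population patients with baseline DLQI of 5 or more, with baseline taken at Visit 2 (Day 1) as in SAP 5.3.1.
- The number excluded for a lower baseline is shown by arm.
- The same analysis on all Efficacy-population patients is kept as a sensitivity analysis.

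A DLQI 0/1 display limited to patients with baseline above 1 may be added as an optional supplement.

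The cost is SAP wording; Day 1 DLQI is already collected. The denominator falls to about 30(1−q) per arm, for example 27 at q = 10% and 21 at q = 30%, and the main result then applies only to patients able to respond. Setting the rule before unblinding avoids a choice of denominator after the results are known.

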### 7.4 Subgroup Analysis

	JSS Medical Research India Private Limited Data Management		
Title: Statistical Analysis Plan-Module I			
SOP Number: JSS-DM-BIS-01	Current Version Number: 1.0	Previous Version Number: Nil	Document Date: 25MAR2021

1. Following analysis will be repeated for subgroup of PASI <20 and PASI ≥ 20 and IGA of 3 and IGA of 4:

- ☐ PASI-50, PASI-75, PASI-90 and PASI-100 responder (as per independent dermatologist assessment only) comparison at week 4, 8, and 12 by Chi-square/ Fisher's exact test

- ☐ Change in PASI score (as per independent dermatologist assessment only) at week 4, 8 and 12 from baseline will be assessed by ANCOVA with baseline as covariate.

- ☐ IGA responder (IGA of 0 or 1; as per independent dermatologist assessment only) comparison by week 4, 8 and 12 by Chi-square/ Fisher's exact test

- ☐ IGA reduction (as per independent dermatologist assessment only) analysis by week 4, 8 and 12 i.e. proportion of the patients with at least 1-point reduction, 2-points reduction, 3-points reduction and 4-points reduction (Only for baseline IGA of 4)

- ☐

2. Patient with Head & neck PASI of 12

- ☐ PASI-50, PASI-75, PASI-90 and PASI-100 responder (as per independent dermatologist assessment only) comparison at week 4, 8, and 12 by Chi-square/ Fisher's exact test

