1.0 SYNOPSIS

Sponsor: Aurigene Discovery Technologies Limited

Name of Study Therapy: AUR101 – An oral ROR_γT inhibitor for anti-inflammatory disorders

Protocol ID: AUR101-201

Title of Study: A Phase II, Multicenter, Double-blind, Double-dummy, Placebo controlled, Randomized, Study to Evaluate the Efficacy and Safety of two doses of AUR101 in patients with Moderate-to-Severe Psoriasis (INDUS-2).

Study Centers: 15-25	Phase of Development:
	Phase II

Study Objectives:

Primary:

• To assess efficacy of AUR101 in patients with moderate-to-severe psoriasis

Secondary:

- To evaluate the safety and tolerability of two oral doses of AUR101 in patients with moderate-to-severe psoriasis
- To evaluate the plasma pharmacokinetics of AUR101 in patients with moderateto-severe psoriasis
- To evaluate effect of AUR101 on quality of life in patients with moderate-tosevere psoriasis

Study Design and Investigational Plan:

This will be a multicenter, double-blind, double-dummy, placebo controlled, randomized study to evaluate efficacy and safety of two doses of AUR101 in patients with moderate-to-severe psoriasis

- Approximately 90 patients with chronic moderate-to-severe plaque psoriasis (defined as Psoriasis Area and Severity Index (PASI) ≥12 and Body Surface Area (BSA) involved ≥10%) will be randomized to the 2 dose groups of AUR101 and placebo in the ratio of 1:1:1.
- The patients in each arm will receive AUR101 of 400 mg twice daily or AUR101 600 mg twice daily or matching placebo twice daily for 12 weeks in a double blind, double dummy fashion. All the patients will be followed up for 14 ± 2 days of their last dose for safety assessment.
- A subset of approximately 25 patients, who consent, will be asked to come for plasma PK assessment in week 4 of dosing.

Inclusion Criteria

- 1. Confirmed diagnosis of chronic plaque-type psoriasis, diagnosed at least 6 months before screening
- 2. Psoriasis of at least moderate severity, defined as PASI≥12 and involved BSA≥10 % at screening and Day 1

- 3. Adult males or females, ≥ 18 to ≤ 65 years of age,
- 4. Ability to communicate well with the investigator and to comply with the requirements of the entire study
- 5. Willingness to give written informed consent (prior to any study related procedures being performed) and ability to adhere to the study restrictions and assessments schedule.

Exclusion Criteria:

- 1. History of erythrodermic, guttate, or pustular psoriasis within last 12 months

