### 5.1 Sample Size Determination

AUR101 doses will be tested versus placebo with respect to the primary endpoint (PASI 75 response). A sample size of 25 in each of the three arms will provide an 80% power with a one-sided Type I error of 0.05, if the true placebo response rate is 7% and the response rate on investigational arm(s) is 35%. The sample size is increased to 30 to account for ~ 15-20% dropouts over the study period. Placebo response rates from previous studies was 4-7% in most of the studies in similar patient population. No multiplicity adjustments were considered in the sample size calculation as it is a POC study.

A subset of approximately 25 consenting patients will participate in the pharmacokinetic part in addition to main study.

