**Title: Statistical Analysis Plan-Module I**

 SOP Number:  
 JSS-DM-BIS-01

Current Version Number: 1.0

Previous Version Number: Nil

 Document Date:  
 25MAR2021

?

Summary descriptive statistics will consist of the number and percentage of responses in each category for discrete variables, and the mean, median, standard deviation (SD), SE, median and 95% confidence interval for continuous variables.

Mean and Median values will be reported to one decimal place. Standard deviation, standard error and 95% confidence interval values will be reported to two decimal places.

Percentages will be rounded to one decimal place. Where appropriate, the number and percentage of responses will be presented in the form XX (XX.X %).

All Adverse Events (AE) and Serious Adverse Events (SAE) will be presented: Number of events, Number of subjects and %(n/N) of subjects.

P-values will be rounded to three decimal places. P-values less than 0.001 will be reported as <0.001 in tables. P-values greater than 0.999 will be reported as >0.999.

P value <0.05 will be considered significant.

All listings will be sorted for presentation in order of site number, patient number, date of procedure or event.

All categories of variables will be presented even if there is no data. Zero frequencies are going to be represented as “0 (0.0%)” in reporting of results.

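### SAP 7.4 tests the treatment effect separately within each baseline PASI and IGA level but never compares the effect between levels, so a uniform effect would often look confined to one level

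*SAP*

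**What the plan says.** SAP 7.4: "Following analysis will be repeated for subgroup of PASI <20 and PASI ≥ 20 and IGA of 3 and IGA of 4". The list that follows covers PASI 50, 75, 90 and 100 responders and IGA responders by chi-square or Fisher, PASI change by ANCOVA with baseline as covariate, and IGA point reductions with no test named. All are at weeks 4, 8 and 12. A second item repeats the PASI responder comparisons in a head-and-neck subgroup.

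SAP 9.1, among the reporting conventions: "P value <0.05 will be considered significant". Subgroup results are not exempted.

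Three other places bear on the point:

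- SAP 7.2 has the only interaction term in the plan, and it is visit by treatment.
- SAP 7.1 has a CMH sensitivity analysis adjusted for site and baseline PASI. It names no test of homogeneity.
- SAP 6.1 tabulates how many patients fall in each PASI and IGA level. No expected proportions are given.

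The protocol's statistical section has no subgroup plan.

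**The concern.** A subgroup analysis asks whether the drug's effect differs between levels. Two separate tests do not answer that. One can fall below 0.05 and the other above it when the effects are identical, and in levels this small that will happen often.

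SAP 1.0 says the analysis is meant to inform the AUR101 development programme, and may feed a sample-size amendment, publications or regulatory submissions. Baseline PASI and IGA are also eligibility variables (Protocol 7.1, 7.2 and 9.3.2), so they are natural candidates for narrowing a later trial. A result that is significant in severe but not in moderate disease could be taken as an effect of severity with nothing behind it.

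**Working it through.** **Inputs (SAP 5.1 unless stated)**

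- "A sample size of 25 in each of the three arms will provide an 80% power", "with a one-sided Type I error of 0.05", with PASI 75 rates of 7% on placebo and 35% on active.
- "The sample size is increased to 30 to account for ~ 15-20% dropouts over the study period".
- Allocation 1:1:1 (Protocol synopsis).
- Threshold p<0.05 (SAP 9.1), two-sided because the alternatives in SAP 7.1 are two-sided.
- Assumptions: the same 7% and 35% in both levels (a uniform effect), and splits from 50:50 to 80:20.

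**1. The plan's own figure.** The normal approximation with 25 per arm and one-sided 0.05 gives power 0.799, so the stated 80% is reproduced. Two-sided it is 0.692.

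**2. Power within each level.** This was found by exact binomial enumeration. The two levels contain different patients, so with powers x and y:

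P(exactly one significant) = x(1−y) + y(1−x)

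Example, 15 + 15 per arm:
- Fisher: 2 × 0.321 × 0.679 = 0.436
- Chi-square: 2 × 0.496 × 0.504 = 0.500

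Example, 12 + 13 per arm:
- Fisher: 0.211 × 0.748 + 0.252 × 0.789 = 0.357
- Chi-square: 0.368 × 0.586 + 0.414 × 0.632 = 0.477

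| Patients per arm | Split | Exactly one, Fisher | Exactly one, chi-square | Both, Fisher | Both, chi-square |
|---|---|---|---|---|---|
| 25 | 12/13 | 36% | 48% | 5% | 15% |
| 25 | 15/10 | 37% | 50% | 4% | 14% |
| 25 | 18/7 | 43% | 55% | 2% | 8% |
| 25 | 20/5 | 49% | 58% | 2% | 10% |
| 30 | 15/15 | 44% | 50% | 10% | 25% |
| 30 | 18/12 | 46% | 52% | 9% | 21% |
| 30 | 21/9 | 51% | 57% | 6% | 17% |
| 30 | 24/6 | 60% | 62% | 1% | 17% |

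In every row, exactly one level significant is more likely than both.

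**3. Sensitivity.** By normal approximation, a placebo rate of 4% or 10% gives 43-56% (splits 50:50 to 70:30). One-sided testing at 0.05 gives 48-54%. Across the two dose comparisons, the chance that at least one shows the pattern for a given split is 63-85% (simulation with random level sizes, 50:50 to 80:20).

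**4. What a between-level contrast would give.** For level sizes a and b per arm, the standard error of the difference between the two risk differences is

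SE = √[(0.35×0.65 + 0.07×0.93)(1/a + 1/b)] = √[0.2926 (1/a + 1/b)]

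- 15 + 15: SE = 0.198, half-width 1.96 × 0.198 ≈ 0.39
- 12 + 13: SE = 0.217, half-width ≈ 0.42
- 20 + 5: SE = 0.270, half-width ≈ 0.53

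Under a uniform effect, this contrast with an Agresti-Caffo variance is flagged in about 2-3% of simulated trials. With a plain Wald variance it is flagged in 6-9% for splits up to 70:30 and 11-13% at 80:20.

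**5. Sparse cells.** The chance of no placebo responder in at least one level is 1 − (1 − 0.93ⁿ)². With 15 per level, 0.93¹⁵ = 0.337, giving 56%. With 12 per level, 0.93¹² = 0.419, giving 66%. An ordinary logistic interaction would often not be estimable.

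**The case against.** A reader might infer that the plan judges subgroups by p-values alone. The documents do not go that far. The within-level ANCOVA yields an adjusted treatment difference. SAP 7.4 says that analyses are repeated, and the PASI responder analyses in 7.1-7.3 carry Clopper-Pearson and Miettinen-Nurminen intervals, so these may come with the repeat. The IGA point-reduction item names no test. This part of the objection stands, but none of these outputs compares one level with the other.

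A reader might also infer that a later population will be chosen from these tests. No text ties such a decision to 7.4. The sentence in SAP 1.0 covers the whole analysis, and the 0.05 rule is a general reporting line. The risk is one of interpretation, which the plan leaves open because it gives no rule for reading subgroup results.

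One could count 4 levels × 18 tests × 2 doses = 144 p-values. That count assumes a separate test per dose, which 7.4 does not state, and it omits the head-and-neck item. The point does not depend on it.

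Expected responder counts per cell are about 2.5-3.2 at 12-15 per arm (21% average rate), so Fisher would normally be chosen and the lower figures for even splits are the more relevant. That is fair, and 36-44% is still high. Finally, this is a proof-of-concept trial with multiplicity control openly waived. That limits the weight of the point but does not make separate tests a comparison of effects.

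**Conclusion.** The concern holds for the missing between-level comparison. At the planning rates, a uniform effect on week-12 PASI 75 makes exactly one level significant in about 36-44% of trials (Fisher) or 48-50% (chi-square) with even splits, and up to about 60% with uneven ones.

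These figures are for one dose, one split and one endpoint at one week, with an assumed split and equal rates in both levels. PASI 90 and 100 would differ, and the ANCOVA of PASI change was not quantified. Because the split is unknown, the even-split figures are not a bound.

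The consequence is limited to subgroup conclusions. The primary analysis does not depend on SAP 7.4.

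**What to change.** For each split (PASI <20 / ≥20; IGA 3 / 4), amend SAP 7.4 to:

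- Report the dose-placebo difference with 95% CI in each level, using Miettinen-Nurminen for responders as in 7.1-7.3.
- Report the between-level contrast with 95% CI. For responders, use the difference of risk differences with a small-sample variance such as Agresti-Caffo. Avoid plain Wald and ordinary logistic regression because of sparse or zero cells. For PASI change, fit one ANCOVA on all efficacy patients with a treatment-by-subgroup term.
- State that a subgroup difference is claimed only from this contrast, and that within-subgroup p-values are descriptive and exempt from the 0.05 rule in SAP 9.1.

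The cost is SAP wording and some extra analysis per endpoint, week and dose. No new data or patients are needed. The contrast will usually be inconclusive, and the wide interval shows readers how little the trial can say about differences between levels.
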